	
Morning of D2:
 
 • Blood sampling n° 4. 
Hospital discharge:
 
 • Parameters of therapeutic management and events that occurred during the admission in an ICU, including maximum SOFA score (if applicable), • PPH management summary 
At 6 ± 2 weeks following delivery:
 
Collection of tolerance data on the IMP during an obstetrical follow-up visit or a phone contact.

DESCRIPTION OF AND JUSTIFICATION FOR DATA COLLECTED
	
Anamnestic parameters:
 
 • Demographic parameters: height, weight prior to pregnancy and last known weight, • History of thromboembolic, obstetrical events and any clinically relevant medical conditions. • Obstetrical parameters of the pregnancy, mainly: 
 ○ Date of last menstrual period, gestational age, levels of Hb of the third trimester of pregnancy, ○ Ht and platelets will be collected if available. 
Delivery parameters:
 
 • Times of the start and the end of delivery and number of live births and/or stillbirths, • Start and end hours of haemorrhage, • Initial obstetrical management of the haemorrhage : artificial delivery, uterine or genital examination, • Any haemostatic intervention (intrauterine balloon, uterine ligation, embolization, vascular ligation, hysterectomy), • Vascular filling (if any): volumes and types of filling solutes since the start of delivery until D2, • Transfusions: types and number of transfused blood products since the start of delivery. 
Clinical events until hospital discharge:
 
 • Duration of stay in the obstetrics room (arrival and discharge hours), • Number of days of hospital stay following delivery, • Number of days in resuscitation and/or intensive care and/or PICU and/or continuous care units, • Number of days with assisted ventilation, • Maximum SOFA score for patients transferred in resuscitation and/or intensive care and/or PICU and/or continuous care units,

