8.2.2. Visit 2: Randomisation and IMP infusion

- Randomisation will be performed as soon as possible after inclusion and after the start of prostaglandins infusion (see Section 8.1.3).
- IMP administration
 - A third party reconstitutes the IMP (see [Section 6.4.2](#)).
 - The start of IMP infusion corresponds to H0 and should be within the 30 minutes following the start of prostaglandins infusion.
 - The start and the end times and the administered volume will be collected in the CRF.
- Concomitant treatments including intravenous fluids and blood products;
- Local tolerance which occurred during IMP infusion and AEs if any.

8.2.3. Visit 3: H2 (120 ± 30 min) / Blood sampling 2

The following data will be collected in the CRF:

- Blood sampling:
 - Complete blood count, Hb, Ht, platelets,
 - Haemostatic profile: fibrinogen, PT, QT, aPTT, D-dimers,
- Vital signs
 - Measurement of arterial blood pressure (systolic and diastolic),
 - Heart rate;
- Haemorrhage parameters:
 - Measured or estimated volume of blood loss from the start of bleeding;
- Concomitant treatments including intravenous fluids, blood products, tranexamic acid and fibrinogen concentrate as rescue therapy: any modification or institution of a new treatment;
- AEs if any.

8.2.4. Visit 4: H6 (360 ± 30 mn) / Blood sampling 3

[figure not shown]
The following data will be collected in the CRF:

- Blood sampling:
 - Complete blood count, Hb, Ht, platelets,
 - Haemostatic profile: fibrinogen, PT, QT, aPTT, D-dimers,
- Vital signs
 - Measurement of arterial blood pressure (systolic and diastolic);
 - Heart rate;
- Haemorrhage parameters:
 - Measured or estimated volume of blood loss from the start of bleeding;
- Concomitant treatments including intravenous fluids, blood products, tranexamic acid and fibrinogen concentrate as rescue therapy: any modification or institution of a new treatment;
- AEs if any.

8.2.5. Visit 5: morning of D2 / Blood sampling 4

Depending on the time of delivery, the assessment in the morning of D2 may differ from H48 (considering that the first blood sampling in hospital is performed around 7h00 in the morning).

H0 = start of IMP administration

Even if the patient has been transferred to another hospital or department within the same hospital, the investigator must ensure that all laboratory analyses will be performed, and the following parameters will be recorded in the CRF:

- Blood sampling:
 - Complete blood count, Hb, Ht, platelets,

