8.2.6. Visit 6: Hospital discharge

Visit 6 corresponds to the final hospital discharge regardless the site of the patient's last admission after delivery and 6 weeks after delivery at the latest.

The data for this visit will also be collected if the patient is prematurely withdrawn after randomisation.

- Date of discharge;
- Date and time of obstetric room discharge;
- Stay in resuscitation and/or intensive care and/or PICU and/or continuous care units during hospitalisation (yes/no); if yes:
 - Length of stay in the unit;
 - Maximum SOFA score during the stay in the unit;
 - Number of days with assisted ventilation;
 - Renal failure that required dialysis;
 - Hypotension episodes that required continuous vasopressor therapy;
 - Acute pulmonary oedema, acute respiratory distress syndrome, transfusion-related acute lung injury (TRALI);
- Haemorrhage parameters:
 - Haemorrhage end date and time;
 - Total volume of blood loss: measured or estimated;
 - Blood-draining containers (if any): date and time of setting and removal and the total volume collected;
 - Possible haemostatic intervention needed: uterine tamponade by compression balloon (Bakri or Belfort-Dildy balloon), uterine compression sutures (B-Lynch suture, multiple squares/rectangles technique of Cho), arterial embolization or ligation, hysterectomy.
- Physical examination;
- Vital signs:
 - Measurement of arterial blood pressure (systolic and diastolic);
 - Heart rate;
- Concomitant treatments including intravenous fluids, blood products, tranexamic acid and fibrinogen concentrate as rescue therapy: any modification or institution of a new treatment;
- AEs if any.

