No interim analysis is planned.

12.10.1. 3. *Secondary efficacy variables*

Analyses of secondary efficacy endpoints will be primarily conducted in the ITT set. Sensitivity analyses will be performed in the PP set. Missing data will not be replaced.

12.10.1. 3.1. Description of secondary efficacy variables

Secondary efficacy variables are listed in [Section 10.1.2](#).

The following parameters will also be derived:

1. Change in plasma fibrinogen level (g/L) between H2 and H0
2. Change in plasma fibrinogen level (g/L) between H6 and H0
3. Change in plasma fibrinogen level (g/L) between D2 and H0
4. The same changes will be calculated for Hb, Ht and RBCs
5. Duration of haemorrhage (hours): end time of haemorrhage – start time of haemorrhage
6. Length of stay in the obstetrics room (arrival and discharge hours)
7. Length of stay in obstetrics units (date of delivery and discharge date)
8. Number of days in resuscitation and/or intensive care and/or PICU and/or continuous care units (admission date and discharge date)
9. Number of days with assisted ventilation

12.10.1. 3.2. Analysis of secondary efficacy variables

Otherwise specified thereafter, all secondary efficacy variables will be compared between the 2 groups using chi-square for categorical data and using t test for continuous quantitative data or other appropriate tests.

Raw laboratory variables (including baseline data) will be presented by randomisation group at each determination (H0, H2, H6 and D2) and shift tables will also be displayed at the same periods. No statistical test will be performed on those data. Determinations at other sampling times will be listed except if other specific times are defined in the SAP.

Changes in laboratory parameters will be presented by randomization group and t test will be performed to test the hypothesis H0: no difference between the 2 randomization groups versus H1: any difference between the 2 randomization groups.

Furthermore, will be compared by t test in the subgroup of patients transferred in resuscitation and/or intensive care and/or PICU and/or continuous care units:

1. Number of days in resuscitation and/or intensive care and/or PICU and/or continuous care units,
2. Number of days with assisted ventilation.

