- 1- Change in plasma fibrinogen level (g/L) between H2 and H0
- 2- Change in plasma fibrinogen level (g/L) between H6 and H0
- 3- Change in plasma fibrinogen level (g/L) between D2 and H0
- 4- The same changes will be calculated for Hb, Ht and RBCs
- 5- Duration of haemorrhage (hours): end time of haemorrhage – start time of haemorrhage

- 6- Duration in the obstetrics room (from arrival hour in obstetrics room to delivery hour)
- 7- Duration of hospitalization (from arrival date in obstetrics room to hospital discharge date)
- 8- Number of days in resuscitation and/or intensive care and/or PICU and/or continuous care units (admission date and discharge date)
- 9- Number of days with assisted ventilation

3.3.6.3.2 *Analyses of secondary efficacy variables*

3.3.6.3.2.1 Analyses of key secondary variables

The analyses of key secondary variables will be tested with the Hochberg step-up method:

- 1- Calculated/estimated volume of total blood loss, 48 hours following IMP administration

The estimated/calculated volume of total blood loss 48 hour after IMP administration will be compared between the Clottafact[®] group and placebo group by a t test or non parametric test.

- 2- Percentage of patients requiring any need for rescue procedure

The percentage of patients requiring any need for rescue procedure within 48 hours following IMP administration will be calculated and chi-square or Fisher exact tests will be used to compare between the Clottafact[®] group and placebo group.

- 3- Percentage of patients requiring the use of intrauterine balloon within 48 hours following IMP administration

The percentage of patients requiring the use of intrauterine balloon within 48 hours following the administration will be calculated and chi-square or Fisher exact tests will be used to compare between the Clottafact[®] group and placebo group.

3.3.6.3.2.2 Other analyses of secondary variables

Other secondary endpoints will be analysed in an exploratory purpose.

3.3.6.3.2.2.1 Analyses of the change from baseline in plasma fibrinogen level, Hb and Ht

The evolution in plasma fibrinogen level, Hb and Ht will be analysed at H2, H6 and D2 following IMP administration with a Mixed Model of Repeated Measurements comparing the Clottafact[®] group and placebo group.

3.3.6.3.2.2.2 Analyses of the evolution of haemorrhage

3.3.6.3.2.2.2.1 Analyses of haemoglobin level

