- The percentage of patients losing at least 3 g/dL of Hb within 48 hours following IMP administration with regards to the Hb reference level will be calculated and chi-square or Fisher exact tests will be used to compare between the Clottafact[®] group and placebo group.
- The percentage of patients with an occurrence of Hb level < 9 g/dL within 48 hours following IMP administration will be calculated and chi-square or Fisher exact tests will be used to compare between the Clottafact[®] group and placebo group.

3.3.6.3.2.2.2.2 Analyses of the number of units of transfused blood units

The number of units of transfused blood products within 48 hours following IMP administration will be calculated for the Clottafact[®] group and placebo group and compared using a Chi-square or generalized Fisher exact test.

3.3.6.3.2.2.2.3 Duration of haemorrhage

The time to the end of haemorrhage (hours) will be summarised by treatment group. The duration of the haemorrhage will be presented using Kaplan-Meier estimates to the end of haemorrhage. A log rank test will be used to compare the duration of haemorrhage curves between the Clottafact[®] group and placebo group.

3.3.6.3.2.2.3 Description of haemostatic intervention

The percentage of patients with haemorrhage leading to the occurrence of morbidity will be compared by treatment group using Fisher exact test. The percentage of patients requiring at least pelvic arteries embolization, surgical vascular ligation, uterine ligation, administration of recombinant activated Factor VII, intrauterine

ballon, and hysterectomy within 48 hours following the IMP administration will be calculated by group.

The time of intrauterine balloon placement will be described as other haemostatic interventions.

Fisher exact tests will be performed to compare the occurrence of haemostatic interventions by treatment groups.

3.3.6.3.2.2.4 Description of maternal morbidity

The maternal morbidity will be analyzed in the subgroup of patients transferred in resuscitation and/or intensive care and/or PICU and/or continuous care units with:

1. *Duration (days) in resuscitation and/or intensive care and/or PICU and/or continuous care units.*
2. *The maximal SOFA score,*
3. *Duration of admission in obstetrics room (hours), duration of hospitalization and number of days with assisted ventilation*

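### SAP item 6 ends obstetrics-room stay at the delivery hour, before randomisation; the population for the stay variables is contradictory, and SAP 2.2 lists none of these departures from the protocol

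*SAP*

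**What the plan says.** **Room stay.** The protocol describes this interval twice with the same end point. The synopsis, under clinical events until hospital discharge, has "Duration of stay in the obstetrics room (arrival and discharge hours". Section 12.10.1.3.1, item 6, has "Length of stay in the obstetrics room (arrival and discharge hours". Section 8.2.6 (Visit 6) collects "Date and time of obstetric room discharge". SAP 3.3.6.3.1, item 6, has instead "Duration in the obstetrics room (from arrival hour in obstetrics room to delivery hour".

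**Stay in the unit or hospital.** Protocol 12.10.1.3.1, item 7, has "Length of stay in obstetrics units (date of delivery and discharge date". SAP 3.3.6.3.1, item 7, has "Duration of hospitalization (from arrival date in obstetrics room to hospital discharge date".

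**Population.** SAP 3.3.6.3.2.2.4 opens with "The maternal morbidity will be analyzed in the subgroup of patients transferred in resuscitation" (the sentence goes on to intensive care, PICU and continuous care units). Its third item then names room stay, hospitalisation and ventilation days, and tests follow. Protocol 12.10.1.3.2 names only unit days and ventilation days for that subgroup.

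**Record of changes.** The secondary-analyses row of SAP 2.2 covers only the repeated-measures model for fibrinogen, Hb and Ht.

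**The concern.** An efficacy variable has to include time after allocation. Women enter this trial only after a vaginal delivery complicated by haemorrhage that needs prostaglandins, so an interval that ends at delivery is a baseline measurement. Reported among the efficacy results, it would look like a null finding on room stay when nothing about treatment had been measured.

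The population raises a separate problem. Transfer happens after randomisation and may depend on treatment; SAP 3.3.6.1.2 itself counts transfer to intensive care among the post-randomisation covariates partly confounded with the treatment effect. Comparing arms among transferred women is therefore not protected by randomisation, and it leaves out the women who were not transferred. If the plan can be read either way, the choice could be made after the data are seen.

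**Working it through.** No figure in the plan needs reproducing for this point. The check sets the texts side by side and adds one illustrative calculation.

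**1. Order of events.** Protocol 1.3.3 and 5.2.1 admit only women with haemorrhage after vaginal delivery. Protocol 8.2.2 states "Randomisation will be performed as soon as possible after inclusion and after the start of prostaglandins infusion". The order is: arrival in the room, delivery, haemorrhage, prostaglandins, randomisation, IMP, room discharge. The protocol's interval runs from the first of these to the last. The literal SAP interval covers only the first two. In the ITT set its true between-arm difference is zero, whatever the drug does.

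**2. Could another part of the SAP supply the right definition?** SAP 6.3 (Durations) has no entry for room stay. Item 6 is the only operational definition, so a programmer would follow it.

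**3. Item 7.** The named endpoint in Protocol 3.2.2.4 and SAP 1.10.2.4 is length of stay in obstetrics units. The SAP's derived variable becomes hospitalisation and starts at arrival instead of delivery. The added time lies before randomisation, so in an ITT comparison it adds noise but no bias.

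**4. Which women?**

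| Source | Population for room and hospital stay |
|---|---|
| Protocol 12.10.1.3 | Mainly ITT; the subgroup is named only for unit days and ventilation days |
| SAP 3.3.6.3 | Mainly ITT for secondary endpoints in general |
| SAP 3.3.6.3.2.2.4 | Listed under transferred women |
| SAP 5.2, table 14.2.5.5.2 | ITT in the title, no subgroup named |

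The table title does not settle the matter. Table 14.2.5.5.4, on SOFA, also carries the ITT label, although the flow-chart footnote in SAP 1.3 limits SOFA to transferred women.

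**5. Was it recorded?** The rows of SAP 2.2 cover analysis sets, baseline presentation, missing data, the primary model, covariates, components, the repeated-measures model and multiplicity. Neither these rows nor the amendment summaries in SAP 2.1 mention the stay definitions or their population.

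**6. What the subgroup reading would cost in precision (illustrative).** SAP 1.11 gives 448 patients with 1.55% excluded from the ITT analysis: 448 × (1 − 0.0155) = 441, about 220 per arm. For a two-sample t test (two-sided 5%, 80% power), the detectable difference in SD units is approximately (1.960 + 0.842) × √(2/n). The exact value uses the noncentral t distribution. Transfer rates are assumed.

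| Set analysed | n per arm | Approximate | Exact |
|---|---|---|---|
| All ITT | 220 | 0.267 | 0.268 |
| 5% transferred | 11 | 1.195 | 1.256 |
| 10% transferred | 22 | 0.845 | 0.865 |
| 20% transferred | 44 | 0.597 | 0.604 |

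Each SD is the one within the set analysed. The rows show lost precision; they do not give the power for one common effect.

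**The case against.** The best defence is that one word is wrong. Elsewhere the SAP treats the variable as a stay (3.3.6.3.2.2.4 and table 14.2.5.5.2), and SAP 4.4 schedules vital signs at discharge from the obstetrics room. A slip is plausible, and the finding on item 6 applies to the literal text. It still needs correcting, because that text is the only definition to program from.

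Room stay is also not a named endpoint. Protocol 12.10.1.3.1 introduces it as an additional derived parameter. That lowers the weight of the point. Protocol 12.2 further promises that the study report will discuss SAP deviations from the protocol. This softens the omission from SAP 2.2 but does not cure it, since an unnoticed change may not reach the report.

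Three stronger readings are tempting, and the documents do not support them:

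- **That the SAP has moved room and hospital stay into the transferred subgroup.** One section lists them there, while the general rule and the table title point to ITT. The SAP contradicts itself and does not settle on the subgroup.
- **That the subgroup test would reject too often.** If treatment changed which women were transferred, and time to delivery were related to severity, a spurious difference in item 6 could arise among transferred women. Its size depends on the transfer rates, that relationship and which transfers are averted. The documents give none of these, so no inflation figure belongs in the finding.
- **That transferred-only tests of unit days and ventilation days are errors too.** Protocol 12.10.1.3.2 plans exactly those tests.

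**Conclusion.** Wrong as written, of minor to moderate severity. Three departures from the protocol stand on the text alone: item 6 ends before randomisation, item 7 starts at arrival instead of delivery, and room and hospital stay are listed under a post-randomisation subgroup that the protocol reserves for two other variables. On the last of these the SAP is inconsistent with itself. SAP 2.2 lists none of them.

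Item 6 carries the most weight: followed literally, it yields a variable that treatment cannot affect. Item 7 costs only some precision if the comparison is made in the ITT set. The loss under the subgroup reading, from 0.27 SD to between 0.60 and 1.26 SD, rests on assumed transfer rates of 5% to 20% and is illustrative.

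A reader might infer that the trial's main conclusions are at risk. They are not: SAP 3.3.2 and 3.3.6.3.2.2 make these variables exploratory, and neither the primary analysis nor the Hochberg family uses them.

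**What to change.** - In SAP 3.3.6.3.1, define item 6 as room discharge minus room arrival.
- In SAP 3.3.6.3.2.2.4, state that room stay and hospital or obstetrics-unit stay are compared between arms in all ITT women.
- Align item 7 with the protocol (delivery date to discharge date), or keep the new start and record it in SAP 2.2 with a reason. Record there any other definition that still differs.
- Report the proportion transferred, by arm, beside the transferred-only results.

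Unit days, SOFA and ventilation days can stay as planned; relabelling them or adding other tests is not part of this correction.

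The cost is a few lines of SAP text and light programming. The room-discharge time is already collected at Visit 6. The protocol's room interval also contains time before the IMP, which adds noise but no bias in the ITT comparison.

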4. SAFETY EVALUATION

Analyses of safety endpoints will be conducted in the safety set (SS).

Missing data will not be replaced.

The standard dictionary for coding adverse events will be the MedDRA (version 17.1).

All AEs will be classified as emergent (i.e. happening or worsening after the time of start of IMP perfusion, defined as treatment-emergent adverse event, TEAEs) or not emergent.

4.1 Summary of AEs and TEAEs

Numbers and percentages of patients will be summarised overall by treatment group, with at least one AE, one serious AE (SAE), one maximal severity AE, one strongest relationship AE, the action taken, the treatment provided and the outcome. The duration of AE will be also presented.

Summary of TEAEs will include the same information as the summary AEs.

4.2 AEs and TEAEs by System Organ Class and Preferred Term

Numbers and percentages of patients with at least one AE and numbers and percentages of patients with at least one emergent AE will be presented by treatment group according to SOC and PT :

- for all AEs,
- for SAEs,
- for AEs related to study treatment,
- for AEs leading to study treatment discontinuation.

The duration of the AE and the duration between the last dose of IMP and onset of the adverse event will be calculated.

Arterial and venous thromboembolic events over the study period will be compared between treatment groups by chi-square tests or Fisher tests.

No statistical tests will be performed on other variables.

The following listings will be produced:

- Individual data listing of related adverse events,
- Individual data listing of adverse events leading to Treatment discontinuation,
- Individual data listing of SAEs,
- Individual data listing of deaths.

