9.2.1. Known and potential risk(s) related to the IMPs

- Clottafact®

As specified in the Risk Management Plan of Clottafact®, the potential risks are:

Thromboembolic events:

Venous and arterial thromboembolic events are the main safety concerns associated with the use of fibrinogen concentrate. However, several minimisation actions are taken in order to limit the potential risks, which are detailed thereafter (see [Section 9.3](#)).

Anaphylactic reactions:

Immunoallergic events and anaphylactic accidents are potential concerns, which will be minimised by patient monitoring during administration.

Immunogenicity:

The occurrence of antibodies against fibrinogen is a very rare complication of fibrinogen replacement therapy. The risk of antifibrinogen antibodies appearance has been described only once in a patient with congenital afibrinogenaemia and rheumatic valvular heart disease.

Viral safety:

Clottafact® is purified from human blood of selected donors and its manufacturing process includes three viral/non-conventional transmissible agents removal/inactivation steps (solvent-detergent, dry heating and 35 nm filtration). Despite these highly secured procedures, the risk of viral infection or non-conventional transmissible agents cannot be totally ruled out.

Standard measures to prevent infections resulting from the use of medicinal products prepared from human blood or plasma include: selection of donors, screening of individual donations and plasma pools for specific markers of infection and the inclusion of effective manufacturing steps for the inactivation/removal of viruses. Despite these safety procedures, when medicinal products prepared from human blood or plasma are administered, the possibility of transmitting infectious agents cannot be totally excluded. This is also applied to unknown or emerging viruses and other pathogens. The previously mentioned measures are considered to be effective against enveloped viruses such as HIV, HBV, HCV and for the non-enveloped viruses HAV and parvovirus B19. There is reassuring clinical experience regarding the lack of hepatitis A or parvovirus B19 transmission and it is also assumed that the antibody content makes an important contribution to the viral safety.

- Placebo

At the planned conditions of use of Clottafact[®] placebo, no risk is expected.

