12.3. Sample Size Determination

It is estimated that, in the control group, 42% of patients will fulfil the primary endpoint (unpublished data from the Pithagore cohort). With an expected percentage of patients in the Clottafact[®] treated group of 27%, the difference between the two groups will be of 15%. With a power (1-β) of 90%, a type I error (α) of 5% and a two-sided test (Z test, unpooled variance), a sample size of 206 patients per treatment group is needed.

The rate of drop-out is assumed to be approximately 5%. Therefore, 434 patients will be included in the study.

As there is some uncertainty about the test Z variance depending itself on the expected rates, the variance will be re-estimated in a blind way at 80% of the initially planned sample size (i.e. 80% of 412=326 evaluable patients or 348 patients with adjustment for a 5% dropout rate) and the sample size will be increased according to the new estimated variance so as to maintain the power to 90% while still considering the same originally planned difference in failure rates, i.e. 15%.

It can be shown that the possible increase in sample size with adjustment for a 5% dropout rate cannot exceed 50 additional patients. Therefore, the new sample size will not exceed 484 patients.“

Of note, as the sample size reassessment is performed in a blind way, i.e. based on an overall estimate of the overall failure rate, it is known to not inflate the type I error of the primary analysis. An additional rule for the reassessment of the sample size is as follows: only an increase (i.e. no decrease) in the sample size will be allowed at the blind interim analysis.

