12.11. Safety Analysis

Analyses of safety endpoints will be conducted in the safety set. Missing data will not be replaced.

With respect to AEs, all AEs occurring during the treatment period will be classified using the Lowest Level Term (LLT), Preferred Terms (PT) and System Organ Class (SOC). The duration of the AE and the duration between the last dose of IMP and onset of the adverse event will be calculated.

The number of patients with at least one AE will be tabulated by treatment group, SOC, PT and LLT. Patients with SAEs, IMP-related AEs and other significant AEs will be tabulated by treatment group, SOC, PT and LLT.

The number of AEs will be tabulated by treatment group, SOC, PT and LLT.

All SAEs, IMP-related AEs and other significant AEs will be listed by treatment group, SOC, PT and LLT.

The standard dictionary for coding events will be the MedDRA (version 16.0).

AEs reported before the start of IMP infusion will only be listed with individual patient's AE data collected, if applicable.

Raw laboratory variables (including baseline data) will be presented by treatment group at each determination (H0, H6 and D2) and shift tables will also be displayed at the same periods. Determinations at other sampling times will be listed except if other specific times are defined in the SAP.

Arterial and venous thromboembolic events over the study period will be compared between treatment groups by chi-square.

No statistical tests will be performed on other variables except if it is needed to explore any AE with possible clinical significance.

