5. TABLES, FIGURES AND GRAPHS

5.1 General Remarks about Tables

This section lists all tables and figures in the order in which they are expected to appear in the statistical report.

Table templates may be adapted as needed at the time the statistical analyses are performed.

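### Thromboembolic events, the main named risk, get a chi-square or Fisher test but no effect estimate, confidence interval or dedicated pooled table

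*SAP*

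**What the plan says.** Protocol 9.2.1 states: "Venous and arterial thromboembolic events are the main safety concerns associated with the use of fibrinogen concentrate". Protocol 9.2.3 repeats that this is the main known risk, and describes the trial's aim as showing benefit from giving the product before low fibrinogen has been demonstrated.

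The planned analysis is one sentence in each document. Protocol 12.11: "Arterial and venous thromboembolic events over the study period will be compared between treatment groups by chi-square". SAP 4.2: "Arterial and venous thromboembolic events over the study period will be compared between treatment groups by chi-square tests or Fisher tests". Neither asks for an estimate or an interval, and neither says whether arterial and venous events are tested together or separately. SAP 4.2 then rules out tests on its other variables, so this is the only between-arm inference on adverse events.

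On outputs, SAP 5.1 says: "This section lists all tables and figures in the order in which they are expected to appear in the statistical report". The safety outputs under 14.3 contain no thromboembolic table. The events do reach other outputs. Protocol 9.5.3 requires deep venous and arterial events to be reported as serious whatever their cause. They therefore enter Table 14.3.3.5 and Listing 14.3.5.3 and, if they start between H0 and hospital discharge, Table 14.3.4.5.

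Protocol 10.2 follows symptomatic thromboembolic events for six weeks after the study product. SAP 6.5 closes the treatment-emergent window at hospital discharge.

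**The concern.** A significance test answers the wrong question for a rare harm. What matters is how large an excess the data still allow, and only an estimate with an interval shows that. For efficacy the SAP does this: odds ratios with 95% intervals are planned for the primary endpoint, its components and the subsets (SAP 3.3.6.2.2 to 3.3.6.2.6). The main named risk has no counterpart.

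The tables that will hold the counts do not fill the gap. Rows by preferred term spread one risk over several lines and do not give the number of patients with at least one event, overall or by venous and arterial type. The treatment-emergent tables also leave out events dated after discharge, which the six-week follow-up is meant to catch.

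At stake is the risk half of the benefit-risk statement for early use. If few events occur, the planned test will probably be non-significant with or without a real excess, and the plan provides nothing beside it to show what remains possible.

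**Working it through.** **Size of the safety set.** The documents size the trial on the primary endpoint only. Protocol 12.3 uses 42% v 27%, two-sided 5%, 90% power and an unpooled Z test:

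n = (0.42 × 0.58 + 0.27 × 0.73) × (1.960 + 1.282)² / 0.15² = 0.4407 × 10.51 / 0.0225 = 205.8

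This matches "a sample size of 206 patients per treatment group is needed". Inflating for 5% dropout, 412 / 0.95 = 433.7, or 434, also matches. SAP 1.11 reports 448 recruited with 1.55% untreated: 448 × (1 - 0.0155) = 441, about 220 per arm. The 89.6% power stated there concerns the primary endpoint and says nothing about thromboembolism.

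**Which test applies.** Protocol 12.2 switches to Fisher when an expected count is below 5. With equal arms the expected count is half the total number of events, so Fisher applies below 10 events in all.

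**Power.** The documents give no thromboembolic rate, so every risk below is an assumption. Power is by exact enumeration of two binomials, n = 220 per arm, two-sided Fisher at 5%.

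| Placebo risk | Active risk | Ratio | Power |
|---|---|---|---|
| 0.25% | 0.75% | 3 | 0.4% |
| 0.5% | 1.5% | 3 | 5% |
| 1% | 3% | 3 | 20% |
| 2% | 6% | 3 | 49% |
| 0.5% | 2.5% | 5 | 24% |
| 1% | 5% | 5 | 62% |
| 2% | 8% | 4 | 80% |

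In the higher-rate rows the total will often reach 10 events and the chi-square test would apply. The normal approximation then gives somewhat more: 57% for 2% v 6%, 69% for 1% v 5% and 82.5% for 2% v 8%.

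**What an interval would show.** These are hypothetical counts, active v placebo, 220 per arm, with Newcombe 95% intervals for the risk difference in percentage points.

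| Events | Fisher p | 95% interval |
|---|---|---|
| 0 v 0 | 1.00 | -1.7 to +1.7 |
| 2 v 2 | 1.00 | -2.4 to +2.4 |
| 4 v 1 | 0.37 | -1.0 to +4.2 |
| 5 v 1 | 0.22 | -0.6 to +4.8 |
| 7 v 1 | 0.068 | +0.1 to +6.0 |
| 8 v 1 | 0.037 | +0.5 to +6.6 |

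For 5 v 1 in full: the risks are 2.27% and 0.45%, difference 1.82 points. The Wilson limits are 0.98% to 5.21% and 0.08% to 2.53%.

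- Lower limit: 1.82 - √[(2.27 - 0.98)² + (2.53 - 0.45)²] = -0.6
- Upper limit: 1.82 + √[(5.21 - 2.27)² + (0.45 - 0.08)²] = +4.8

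Fisher first falls below 0.05 at 6 v 0 (p = 0.030) or 8 v 1.

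**The case against.** The strongest reply has four parts.

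1. **The counts will be reported.** A reader might infer that the risk is reduced to a bare p-value with no table behind it. The documents do not support that. The events are always serious, SAP 4.2 plans numbers and percentages of patients by group and preferred term, and an individual listing is planned. Table 14.3.3.5 is not limited to the treatment-emergent window. SAP 5.1 also lets table templates be adapted. This stands, and narrows the gap to a missing estimate, interval and pooled table. Freedom to adapt a template does not, however, pre-specify an analysis.

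2. **The power figures rest on assumed rates.** A reader might infer that the test will be non-significant whatever the true effect, or that any several-fold excess would be missed. Neither follows: power is 62% for 1% v 5% and 80% for 2% v 8%. The point holds for low event rates.

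3. **Low power for a rare harm is not an analysis error.** The trial is sized on efficacy, no passage says that non-significance would show safety, and an independent data and safety monitoring board reviews serious events (Protocol 3.5.2). All true. But board review during the trial does not tell readers of the final report how large an excess remains possible.

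4. **The choice of interval is partly preference.** This also stands. Any interval suited to rare events would serve.

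**Conclusion.** The point holds in this form: the main named risk has a planned test but no effect estimate, no confidence interval and no dedicated pooled table, and the event has no preferred-term definition.

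The size depends on an event rate that the documents do not give. Over assumed placebo risks of 0.25% to 2%, Fisher power for a tripling runs from 0.4% to 49% at about 220 per arm. At such rates a non-significant p is compatible with an excess of several percentage points, as 5 v 1 shows. If events prove more common or the excess larger, the test becomes informative, and the case for the interval rests on clarity more than on low power.

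This is a worthwhile, cheap improvement to reporting. It does not undermine the efficacy analysis or the collection of safety data.

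**What to change.** In SAP 4.2, with Protocol 12.11 brought into line and the change recorded in SAP 2.2:

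- Fix the list of preferred terms that count as venous and as arterial events before unblinding. State whether superficial venous events count, since the serious-event rule in Protocol 9.5.3 names deep venous and arterial events only.
- Report, per arm in the safety set, patients with at least one event (any, venous, arterial) from H0 to the end-of-study contact, not cut at discharge.
- Give the risk difference with a 95% interval suited to rare events, for example Newcombe or Miettinen-Nurminen, and keep the Fisher p-value beside it.
- Base the safety statement on the interval, chiefly its upper limit, and not on non-significance. Say so in advance, because the two can disagree at the margin: 7 v 1 gives p = 0.068 while the Newcombe interval just excludes zero.
- Add the table to section 14.3 of the list in SAP 5.2.

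The cost is a few lines of text and code, one table and a short blinded review of terms. No new data are needed. The downside is that the report will probably have to say openly that a modest excess cannot be excluded. The change adds no power.
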